#### **6.4.2 Serious Adverse Event Reporting**

All SAEs are to be marked in EDC as an SAE. However, sites are not expected to complete the SAE forms if the event occurs while subject is in the ICU. If an event is serious while not in the ICU, regular reporting of SAEs will occur (SAE forms completed and forwarded to MM immediately).

[name]  
Medical Monitor  
E-mail: [[contact]](mailto:[contact])  
[contact]  
[contact]

#### 24-hour Emergency Contacts:

Medical Monitor [name] [contact] or Medical Director [name], MD [contact]

SAEs occurring during the study period, from the initiation of USB002/placebo infusion up to Day 60, will be recorded.

SAEs experienced by subjects enrolled into the study, who are not transferred to the ICU, will be reported according to standard regulatory requirements and guidelines.

For all patients enrolled outside ICU but progress and end up in ICU: all SAEs that occur prior to ICU admission should be recorded and reported per usual requirements, any SAE that occurs after ICU admission will be recorded as an SAE in the EDC but no SAE form will be required to be submitted. Should the Medical Monitor require further information that will be requested directly.

For all patients enrolled when already in ICU, all events are to be recorded as an SAE in the EDC but will not require reporting on an SAE form unless the Investigator feels the event was not a consequence/progression of COVID, in which case the event should be reported on an SAE form per standard practice.

For all those patients discharged from ICU, all SAEs that occur after discharge are to be recorded and reported per standard practice.

The Sponsor will request additional information or documentation as required. As applicable, the Investigator should provide the following documentation at the time of notification if available:

- SAE Report Form;
- Concomitant medication (supporting documents);
- Relevant diagnostic reports;
- Relevant laboratory reports;
- Hospitalization notes;
- Hospital discharge summary (if available).

Due to the high rate of expected clinical deterioration in the ICU group of patients, the following anticipated adverse events/interventions associated with COVID-19 infection will be reported to the Sponsor immediately via email:

- Abnormal pathology results from presentation (including inflammatory markers related to a hyperinflammatory response)
- Secondary infection
- Renal failure
- Cardiac disease e.g., arrhythmias, right heart failure
- Intubation and ventilation
- Venous thromboembolism/arterial thrombosis
- Other clinically significant end organ damage, either biochemical e.g., acute kidney injury, liver impairment, or clinical e.g., stroke
- Death from COVID-19

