## **4. PATIENT SELECTION CRITERIA**

### **4.1. Inclusion Criteria**

1. Signed informed consent from patient or legal representative;
2. Age 18 or greater;
3. Positive reverse transcription polymerase chain reaction (RT-PCR) for SARS-CoV-2 ( $\leq 10$  days of start of infusion);
4. Respiratory rate  $> 20$  RR;
5.  $\text{SpO}_2 < 94\%$  on room air, requiring supplemental oxygen, on mechanical ventilation for  $< 72$  hours (at time of informed consent);

*If screening and infusion occur on the same day, the first  $\text{SpO}_2$  taken at the time of screening needs to be  $< 94\%$  to satisfy eligibility (patient will be put onto oxygen immediately); if screening and infusion occur on separate days, confirm sustained  $\text{SpO}_2 < 94\%$  on room air prior to infusion –if on supplemental oxygen just prior to infusion and  $\text{SpO}_2 < 94\%$  then patient automatically meets the criteria.*

6. Chest X-ray confirming bilateral pulmonary infiltrates;
7. Body mass index of  $\leq 40$  units/kg/m $^2$ ;
8. Adequate method of birth control for subjects of child-bearing potential.\*

*\* Note: A female patient is considered to be of childbearing potential unless she has had a hysterectomy, is at least one year postmenopausal or has undergone tubal ligation. For the purposes of this study, adequate birth control includes at least one medically*

*approved and highly effective method of birth control, defined as those which result in a low failure rate (i.e., < 1% per year) when used consistently and correctly, such as implants, injectables and oral contraceptives combined with the use of double condoms. Only male patients whose vasectomy has been confirmed by semen analysis at least 3 months after the vasectomy are allowed not to use acceptable contraceptive methods.*

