### **6.1.2. Definition of Serious Adverse Events (SAE)**

An SAE is any AE that meets at least one of following criteria:

- Is fatal;
- Is life-threatening; in the opinion of the Investigator, the subject was at substantial risk of dying at the time of the adverse event, or use or continued use of the medical product might have resulted in the death of the patient;
- Is a persistent or significant disability or incapacity;
- Requires hospitalization or prolongs an existing hospitalization. Hospitalization will be defined as such if > 24 hours, or a hospitalization that requires an intervention to treat emergent symptomatology (non-diagnostic);
- Exposure prior to conception or during pregnancy may have resulted in a congenital anomaly or birth defect in the child;
- Other important medical events not noted in events above, but may be considered a serious experience when, based upon appropriate medical judgment, may jeopardize the subject and may require medical or surgical intervention to prevent one of the outcomes as listed in #1-5 in this definition.

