8.2.1. Adverse Events

Only treatment emergent adverse events (TEAEs) will be summarized. Summaries will be provided by dose level cohort with all placebo groups combined. Following summaries will be provided:

- Overview of TEAEs - include the total number of TEAEs, serious TEAEs, DLT, and TEAE leading to death
- TEAEs by MedDRA System Organ Class (SOC) and Preferred Term (PT)
- TEAEs by MedDRA SOC, PT, and severity
- TEAEs by MedDRA SOC, PT, and relationship to treatment
- TEAEs by MedDRA SOC, PT, and outcome
- Serious TEAEs by MedDRA SOC, and PT
- TEAE leading to death
- DLT.

All these summaries will include the counts and frequencies of events, and of subjects who had events.

All TEAEs will be listed by subject. Serious TEAEs, TEAEs leading to death, and DLTs will be listed separately.

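### For subjects already in the ICU at enrolment, the protocol's wording has every event recorded as an SAE, so the serious flag needs checking before the serious TEAE tables are built

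*Protocol*

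**What the plan says.** Protocol 6.1.2 makes seriousness depend on listed criteria: "An SAE is any AE that meets at least one of following criteria". Being in the ICU is not among them. Protocol 6.4.1 lists seriousness among the items recorded for every AE, and 6.4.2 opens with the general rule: "All SAEs are to be marked in EDC as an SAE".

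The later text of 6.4.2, after the emergency contacts, sets rules by ICU status:

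- Enrolled outside the ICU and later admitted: "any SAE that occurs after ICU admission will be recorded as an SAE in the EDC but no SAE form will be required".
- Already in the ICU at enrolment: "all events are to be recorded as an SAE in the EDC". The sentence goes on to waive the SAE form unless the investigator thinks the event was not due to COVID.
- After ICU discharge: "For all those patients discharged from ICU, all SAEs that occur after discharge are to be recorded and reported per standard practice".

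Such patients are eligible. Inclusion criterion 5 in Protocol 4.1 reads "requiring supplemental oxygen, on mechanical ventilation for" less than 72 hours, and 6.4.2 itself provides for enrolment in the ICU.

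SAP 8.2.1 plans a serious TEAE count in the overview, a table of "Serious TEAEs by MedDRA SOC, and PT", and a separate listing of serious TEAEs. Summaries are by dose cohort, with placebo combined.

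**The concern.** One of the three ICU rules uses a wider term than the other two. A site that followed it to the letter would flag a mild, non-serious AE as serious if the subject entered the trial from the ICU, and would not do so for the same event in a subject admitted to the ICU a day later. The flag would then partly record place of enrolment.

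Safety and tolerability is the primary endpoint (SAP 4.2), and serious TEAEs are among its main displays. Dose groups are very small: three on USB002 per cohort by plan, and only three subjects in all enrolled in Cohort 4 (SAP 2). One wrongly flagged subject would be visible in such a table.

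**Working it through.** The plan gives no figure to reproduce. The check is a comparison of texts, followed by an illustration on assumed rates.

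**1. Does the exception in the sentence limit the flag?** No. It decides whether an SAE form is sent. What is recorded in the EDC is settled in the first half of the sentence, without qualification.

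**2. Do the neighbouring rules agree?** No. The rules for later ICU admission and for ICU discharge both start from events that are already SAEs. Only the rule for enrolment in the ICU starts from all events.

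**3. Does a later step re-apply the 6.1.2 criteria?** None is stated. SAP 7.2 derives the treatment-emergent flag but has no row for serious; it refers complete derivations to the SDTM and ADaM specifications. SAP 5.1 reconciles SAEs with the pharmacovigilance database, working with the Medical Monitor. ICU events put down to COVID need no SAE form, so that step is not shown to re-test seriousness.

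**4. Which outputs would carry the flag?** Of the eight summaries listed in SAP 8.2.1, two: the serious line of the overview and the serious TEAE table. The separate serious listing carries it too.

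**5. Illustration of size.** Let f be the share of subjects enrolled in the ICU, a the probability of at least one TEAE, and s the probability of at least one TEAE that meets the criteria. All three are assumptions. For simplicity a and s are taken as equal inside and outside the ICU. Under the literal rule:

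- Tabulated share with a serious TEAE = f·a + (1 − f)·s.
- Excess over s = f·(a − s).

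With a = 0.7 to 0.9 and s = 0.2 to 0.4, a − s runs from 0.3 to 0.7:

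| f | Excess, percentage points |
|---|---|
| 0 | 0 |
| 0.10 | 3 to 7 |
| 0.25 | 7.5 to 17.5 |
| 0.50 | 15 to 35 |

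One more ICU-enrolled subject in a dose group of three moves that group's expected share by (a − s)/3, or 10 to 23 points. In counts, an ICU-enrolled subject with only non-serious AEs moves a group from 0/3 to 1/3. A hypothetical subject with six AEs, one of them serious, would add six serious events instead of one.

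If s is higher in ICU patients than elsewhere, as is plausible, a − s is smaller for them and so is the excess.

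**The case against.** The strongest reply is that the sentence sits in a section on SAE reporting, so its events may simply be SAEs. The rest of the sentence supports this: read literally, a mild AE unrelated to COVID would need an SAE form under standard practice, yet standard practice asks for forms only for serious events. The 6.1.2 definition still stands, and the CRF Completion Guidelines (Protocol 9.1) may have settled the matter. This reply has force, and the literal reading cannot be called the intended one. But nothing in the two documents says so, and if sites read the sentence differently the flag is uneven. Either way the flags need the same check.

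It is also fair that the SAP does not say how serious is derived. Use of the EDC flag is the natural reading, but an inference.

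A reader might go further and infer that a chance ICU imbalance would pass for a dose effect, or that escalation decisions were distorted. The documents do not support either:

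- Allocation is randomised and blinded, so no arm is favoured systematically. SAP 7.4 makes no statistical inference.
- The TEAE tables combine placebo across cohorts, so three-against-three comparisons within a cohort are not what they show.
- Subjects are counted as well as events, so an excess of events in one subject would be visible.
- Protocol 6.6 does give the DSMB reports drawn directly from the EDC. But Protocol 6.1 ties a potential DLT to relatedness and leaves its definition to the safety management plan, not to the seriousness flag.

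**Conclusion.** The concern holds as a conflict of wording that leaves the seriousness flag unverified for one group of subjects. If the sentence was followed literally or unevenly, the serious TEAE counts and listing would contain events that met no 6.1.2 criterion, according to ICU status at enrolment.

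The size cannot be stated. The documents give neither the number enrolled in the ICU nor any AE rates, so the figures above illustrate the mechanism and do not estimate it. Error from over-flagging runs towards too many serious events.

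The point is limited to serious TEAEs. It does not put the rest of the primary safety analysis in doubt, but it merits a check before lock because in groups this small a single flag changes the table.

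**What to change.** 1. Reconcile Protocol 6.1.2 with the two parts of 6.4.2 and record which reading applied. Enrolment has stopped (SAP 2), so a wording change alone would not repair data already collected.
2. Before lock and unblinding, identify ICU-enrolled subjects from the ICU admission date collected in the history (Protocol 5.4.1). Have the site confirm that the subject was still in the ICU at enrolment, since the listed history items do not include an ICU discharge date.
3. List every AE flagged serious in those subjects. By query, with the sites still blinded, ask which 6.1.2 criterion each event met.
4. State in SAP 8.2.1 or the ADaM specification that the serious TEAE overview line, table and listing use the confirmed flag.
5. If any flag cannot be confirmed, state the recording rule in the study report and show serious TEAEs by ICU status at enrolment.

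The cost is one query listing in 21 subjects and a sentence in the analysis specification. A formal protocol amendment would also need IRB submission (Protocol 10.1), but the data check does not depend on it.

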#### **6.4.3 Reporting of Pregnancy**

A female patient is of childbearing potential unless she has had a hysterectomy, is at least one year postmenopausal, or has undergone tubal ligation. All sexually active patients must use a reliable method of birth control until Day 60. Any pregnancy occurring in a subject or a subject's sexual partner during the study must be reported to US Biotest as soon as the Investigator is aware of it. The pregnancy will not be considered an SAE; however, information on the event will be collected and the outcome followed to birth or termination of pregnancy.

Any pregnancy complication or premature terminations including miscarriage, spontaneous abortion, or elective termination of a pregnancy for medical reasons will be reported as an SAE, as described in Section 6.4.2. Should the pregnancy result in a congenital anomaly or birth defect, a separate SAE report must be submitted. Furthermore, all neonatal deaths that occur within 30 days of the birth should be reported as SAEs, without regard to causality. In addition, any infant death that occurs after the 30-day reporting period that the Investigator suspects is related to the in-utero exposure to the study treatment should also be reported.

#### **6.5 Study Halting Rules**

This study is a Phase 2 dose escalation study. Dose escalation will be determined following review of the safety and tolerability data in a cohort by the DSMB (see Section 6.6). Following review, at any time point, the study may be terminated. Should this occur,

all subjects who have received treatment will be followed for safety up to Day 60. The Sponsor is responsible for notifying FDA of any temporary halt to the study or when the study is terminated. The Investigator will be required to notify the IRB accordingly.

## 6.6. Safety Oversight

Safety will be overseen by the MM and the DSMB. The DSMB will be comprised of three medical experts, at least one of whom is an infectious disease specialist, and will be supported by a Statistician, who will not be a voting member. The DSMB will be independent and external to the Sponsor and study personnel. DSMB meetings will be conducted per the DSMB charter.

All subject study data will be captured in an EDC system, allowing real-time access to safety and tolerability data and prior to proceeding to dose escalation.

Prior to dose escalation, the DSMB will convene to review the cohort data, and generate a report outlining safety concerns from the subjects' EDC data. This review will be conducted prior to proceeding with either addition of more subjects to a current cohort or proceeding to dose escalation in the next cohort. Assessment of progress and safety, as well as decision to dose-escalate, de-escalate, or increase the number of subjects in any group will be made by a DSMB and recorded in the DSMB meeting minutes as described in the SMP.

The DSMB will evaluate data for each cohort after all 6 subjects in the cohort have completed 96-hours of the USB002/placebo infusion. During the safety review, DSMB members will review all EDC safety data available; provided as reports generated directly from the EDC system and by the Data Management group. Emphasis will be placed on emerging safety trends or events which may constitute DLT (See Section 6.1).

Enrollment will be halted during the cohort data review. If the DSMB determines there is a reasonable safety concern, further enrollment and dose escalation may be delayed or halted. Escalation will continue until Part 1 enrollment is completed and the MTD is determined for Part 2.

In Part 2, DSMB safety reviews will be conducted every 6 weeks. As with Part 1, the DSMB may decide to halt or delay enrollment at any time during Part 2.

## 7. STATISTICAL CONSIDERATIONS

### 7.1 Statistical and Analytical Plans

Formal Statistical Analysis Plans (SAP) will be prepared for each part (1 and 2) of this trial and will be signed off prior to study database lock and prior to any unblinding procedures. Part 1 will detail parameters and interpretation of safety and efficacy signals for dose escalation randomization groups (SOC plus USB002 and SOC plus placebo). Part 2 will detail parameters and interpretation of preliminary efficacy outcomes of the

randomized groups. Any deviations to the planned analyses specified within the SAP will be justified in writing and presented in the final clinical study report.

In Part 1, the data summaries, which will be supported with by-subject listings, will focus on the dose group for SOC plus USB002 as compared to the SOC plus placebo as well as time in trial.

In Part 2, preliminary efficacy assessments will compare the endpoints for the two treatment groups for a signal of efficacy including: time without mechanical ventilation, all-cause mortality, survival at discharge, absence of respiratory failure, responders according to OSCI (see Appendix 1). Data relating to efficacy response will be listed and summarized by dose cohort and time point, as appropriate. On each measurement day, the worst OSCi score will be recorded. Since the efficacy objective of this study is to assess the preliminary efficacy signals, statistical inference (e.g. p value) from the efficacy analyses will be used to assess the strength of the efficacy signals, and will not be adjusted for multiple comparisons. Unless specified in the analyses of efficacy endpoints (see Section 7.2.1), missing data will not be imputed.

## 7.2 Description of Statistical Methods

### 7.2.1 Analysis of the Efficacy Endpoint(s)

Efficacy assessments will be based on the safety analysis set, which is defined as all subjects who have received at least one dose of study medication. Data relating to efficacy response will be listed and summarized by treatment group and time point, as appropriate. Any efficacy related outcomes in Part 1 will be present descriptively and will be detailed in the SAP.

Summary statistics (mean, median, standard deviation, minimum, and maximum) and change from baseline to each scheduled study assessment for ventilator readings will be presented by treatment group. Baseline is defined as the latest non-missing assessment prior to the first study drug infusion.

The primary efficacy outcome, time to peripheral capillary oxygen saturation ( $\text{SpO}_2$ )  $\geq 94\%$  on room air, sustained for at least 48 hours, through Day 28, will be estimated and compared between the two treatment groups using Kaplan-Meier (KM) analysis. Subjects who do not achieve  $\text{SpO}_2 \geq 94\%$ , sustained for at least 48 hours, or die by Day 28 will be censored at Day 28. As a supplemental analysis, an analysis using a Cox proportional hazards model incorporating the baseline covariates: age, baseline severity, and comorbidity, will be performed.

The secondary efficacy outcome of proportion of subjects with all-cause mortality within 60 days from start of treatment, will be compared between the two treatment groups using Fisher's exact test. In addition, as a supplemental analysis, a logistic regression analysis will also be performed to adjust for the same baseline covariates in the primary efficacy outcome analysis: age, baseline severity, and comorbidity.

The secondary efficacy outcomes that are binary, e.g., subjects weaned from mechanical ventilation within the 28-day, subjects progressing from non-invasive (at baseline) to mechanical ventilation, the proportions will be compared using Fisher's exact test. Death will be considered unfavorable outcome for these analyses, i.e. death prior to Day 28 will be considered as on mechanical ventilation. In addition, analysis of subjects weaned from mechanical ventilation will be conducted on those who were on mechanical ventilation at baseline, and analysis of subjects progressing from non-invasive to mechanical ventilation will be conducted on those who were not on mechanical ventilation at baseline. Time to hospital discharge will be analyzed using Kaplan-Meier method. Subjects who are not discharged by Day 28 or die will be censored at Day 28 for the analysis.

All other secondary outcomes will be presented descriptively.

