**5.4.5 Hospital Discharge Prior to Day 28**

If a subject is discharged from hospital earlier than Day 28, Telemed visits will be conducted once a week until Day 28, with the first occurring approximately 7 days after discharge. The Day 28 and Day 60 Telemed visits will occur on Days 28 and 60, respectively, regardless of when the subject is discharged from hospital and the timing of their previous weekly Telemed visits. Part 1 subjects discharged prior to Day 28 will not return to the site for visits (may apply to any of Days 7, 9, 12, 14, 16, 18, 21, or 24, depending on day of discharge) or undergo the procedures regularly scheduled for those visits. Part 2 subjects discharged prior to Day 28 will not return to the site for visits (may apply to Days 18, 21, or 24, depending on day of discharge) or undergo the procedures regularly scheduled for those visits.

Data from the Telemed visits post-discharge will be captured in the EDC.

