5. If subject is discharged from hospital, Telemed visits will be conducted once a week until Day 28, with the first occurring approximately 7 days after discharge. Day 28 and Day 60 Telemed visits will occur on Days 28 and 60, respectively, regardless of discharge date and timing of previous Telemed visits. Discharged subjects will not attend the site for visits (Days 7, 9, 12, 14, 16, 18, 21, or 24, as applicable to discharge day) or undergo procedures scheduled for those visits.
6. Telephone follow-up, if discharged. Day 28 phone call window = +/- 3 days; window not applicable if still hospitalized.

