## APPENDIX 1: ORDINAL SCALE FOR CLINICAL IMPROVEMENT (OSCI)

Score	Patient State	Descriptor
0	Uninfected	No clinical or virological evidence of infection
1	Ambulatory	No limitation of activities
2		Limitation of activities
3	Hospitalized; Mild Disease	Hospitalized, no oxygen therapy
4		Oxygen by mask or nasal prongs
5	Hospitalized; Severe Disease	Non-invasive ventilation or high-flow oxygen
6		Intubation and mechanical ventilation
7		Ventilation + additional organ support – pressors, renal replacement therapy, ECMO
8	Dead	Death

WHO R&D Blueprint novel Coronavirus: COVID-19 therapeutic trial synopsis. 2020 Feb 18.

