7.2. Calculated Outcomes

The following are key endpoints derived from data captured at the sites via the EDC system. Complete documentation of the calculations and data manipulation required to go from the CRF database to the analysis database are contained in the companion documents – SDTM Programming Specification File (SDTM Spec) and ADaM Programming Specification File (ADaM Spec).

Outcome	Calculation	Comment
Study Day	= the days from Day 1 (Date of the First Study Infusion) to the event date	
Time in Trial (days)	= Study completion/withdrawal date – date of informed consent date + 1 day	
Time on Treatment	= Date of last infusion – Date of first infusion + 1	
Baseline value	= Value reported prior to the first study treatment	If multiple values collected prior to the first infusion, non-missing value closest to the date/time of the first infusion is considered as baseline value
Change from Baseline	= Value collected at time point (Visit) – Baseline value	
BMI	= $10000 * (\text{Weight in kg}) / (\text{Height in cm})^2$	Value will be rounded to keep one decimal point
Treatment Emergent Adverse Event (TEAE)	= No, if onset date/time AE is before the date/time of the first study infusion = Yes, otherwise	According to conservative rule, all AEs that cannot be determined as started before the first study infusion will be considered as TEAE

Outcome	Calculation	Comment
Time from baseline to achieving $\text{SpO}_2 \geq 94\%$ on room air	= Date of first achieving $\text{SpO}_2 \geq 94\%$ on room air – Date of first infusion + 1 = null if the subject did not achieve $\text{SpO}_2 \geq 94\%$ till study termination	
Number of ventilator-free days	= the number of days between Day 1 and Day 28 that subjects are both alive and free of mechanical ventilation	
Weaned from MV (Yes/No)	= Yes, if the subject was on MV and then weaned from MV through Day 28 = No, if the subject was on MV and kept using MV till Day 28 = null, if the subject did not use MV from Day 1 to Day 28	
Progressed to MV (Yes/No)	= Yes, if the subject progressed from non-invasive (at baseline) to MV on/before Day 28 = No, if the subject was keeping non-invasive till Day 28	
Time to Progression (TPP)	= First MV date – Date of first infusion + 1 = null, if the subject was keeping non-invasive till Day 28	
Time to hospital discharge	= Hospital discharge date – Study Day 1 + 1 = null if the subject was staying in hospital till Day 28	

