8.2. Primary Outcomes

The primary endpoint of the study will be safety and tolerability, as demonstrated by adverse events (AE), changes in laboratory assessments, ECG assessments, vital signs, and concomitant medications (inotropes and vasopressors). These outcomes will be summarized by cohort. See details in sections 8.2.1 to 8.2.6.

Co-primary endpoint is the difference between USB002 and placebo groups in time to peripheral capillary oxygen saturation (SpO₂) $\geq 94\%$ on room air, sustained for at least 48 hours, through Day 28. All peripheral capillary oxygen saturation (SpO₂) results from baseline to Day 28 will be listed (and summarized if applicable). See section 8.2.7.

No statistical inference will be made for primary endpoint.

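### The 48-hour room-air recovery endpoint has no rule for discharge before the 48 hours are confirmed, and the SAP derivation drops the 48 hours, so the two documents score the same subject in opposite ways.

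*Protocol*

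**What the plan says.** **Definition.** Protocol 2.1.1 and 7.2.1 require room-air SpO2 of at least 94%, held for 48 hours, by Day 28. For the Kaplan-Meier comparison in 7.2.1, subjects who do not achieve SpO2 ≥ 94% "sustained for at least 48 hours, or die by Day 28 will be censored at Day 28". The same section says Part 1 efficacy will be descriptive and detailed in the SAP.

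**After discharge.** Protocol 5.4.5: "Part 1 subjects discharged prior to Day 28 will not return to the site for visits", and they do not undergo the procedures of those visits. A footnote to the Part 1 schedule repeats this. Contact continues by weekly Telemed, and "Data from the Telemed visits post-discharge will be captured in the EDC", but no SpO2 reading is listed for those contacts.

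**Missing data.** Protocol 7.1 bars imputation unless 7.2.1 provides for it, and 7.2.1 says nothing about discharge. SAP 5.3 also bars imputation and assumes data are missing at random.

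**SAP.** Section 8.2 states: "Co-primary endpoint is the difference between USB002 and placebo groups in time to peripheral capillary oxygen saturation" at or above 94% on room air, "sustained for at least 48 hours, through Day 28". Section 4.2 agrees. In 7.2, however, the time is the date room-air SpO2 first reaches 94%, minus the date of first infusion, plus 1. It is "null if the subject did not achieve" that level by study termination. Neither 7.2 nor 8.2.6 contains a 48-hour condition. Section 6, which lists changes from the protocol, does not mention this one.

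**The concern.** Going home on room air is a good outcome on the trial's other measures. Time to discharge is a secondary endpoint. The OSCI in Protocol Appendix 1 places ambulatory states (scores 1 and 2) above "Hospitalized, no oxygen therapy" (score 3). Yet under protocol 7.2.1 a subject kept in hospital off oxygen can complete the 48 hours, while one discharged sooner cannot. The information is lost because the subject went home well, which also sits badly with the missing-at-random statement in SAP 5.3.

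The SAP derivation errs the other way. It credits the early-discharged subject, but also anyone with a single qualifying reading who then returns to oxygen. A reader of SAP 4.2 or 8.2 would expect a 48-hour endpoint and be shown a first-reading endpoint. At stake is what the recovery summaries mean, both overall and within cohort.

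**Working it through.** There is no planned figure to reproduce: protocol 7.3 says the sample size does not rest on power. The check is a trace of subjects through both rules, followed by illustrations.

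**1. Who is exposed.** Infusion stops for recovery only after 48 hours at target on room air, otherwise at 96 hours in Part 1. A 24-hour observation period follows any stop (protocol synopsis and section 3). If that course is followed in hospital, a subject who reaches target at hour t stays until at least the smaller of t + 48 + 24 and 96 + 24 = 120. The 48 hours are complete if t + 48 ≤ 120, that is, t ≤ 72. Exposure is therefore mainly recovery after about hour 72, plus subjects whose treatment ends early. Protocol 5.4.4 foresees discharge before Visit 5.

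**2. Trace.**

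| Subject | Protocol 7.2.1 | SAP 7.2 / 8.2.6 as written |
|---|---|---|
| Reaches target Day 5, holds it 48 hours in hospital | Event | 5 − 1 + 1 = 5 days |
| Reaches target Day 5, home on room air Day 6 | No event, carried to Day 28 | 5 − 1 + 1 = 5 days |
| One reading at target on Day 3, back on oxygen Day 4 and not at target again | No event, carried to Day 28 | 3 − 1 + 1 = 3 days |
| Never reaches target, or dies without reaching it | No event, carried to Day 28 | Null |

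The protocol groups the second subject with the fourth. The SAP groups the third with the first. Neither separates all four as the stated 48-hour endpoint intends.

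**3. Possible size under the protocol rule (all rates assumed).** Let p be true Day-28 recovery and f the share of recoverers discharged before 48 hours are confirmed. Observed recovery is p × (1 − f).

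- p = 80% vs 60%, f = 0: difference 20 points.
- Same p, f = 10%, 20%, 30%, 40% in both arms: 72 − 54 = 18, 64 − 48 = 16, 56 − 42 = 14, 48 − 36 = 12 points.
- Same p, f = 30% vs 10%: 0.80 × 0.70 = 56% vs 0.60 × 0.90 = 54%, difference 2 points.
- p = 70% in both arms, f = 30% vs 10%: 0.70 × 0.70 = 49% vs 0.70 × 0.90 = 63%, a spurious −14 points.

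With exponential recovery times, a true median of 8 days and f unrelated to timing, Day-28 recovery is 1 − 2^(−28/8) = 91%. It falls to about 82%, 73%, 64% and 55% for f = 10% to 40%.

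**4. Size under the SAP derivation as written.** f has no effect, because the first reading already counts. The error there is the number of transient readings, for which the documents give no rate.

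**5. Leverage.** SAP 8.1 and 8.2.6 plan within-cohort comparisons. Full cohorts are three against three, so one reclassified subject moves an arm by 1/3 = 33 points. SAP section 2 reports 21 subjects enrolled, with only 3 in Cohort 4.

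**The case against.** The strongest reply is that the SAP governs these data. All 21 subjects are Part 1, the Part 2 analyses are cancelled (SAP 6.1), and SAP 7.4 rules out inference. The Kaplan-Meier rule with Day-28 censoring will therefore not be applied, and under SAP 7.2 the subject sent home early does receive a recovery time. This stands. A reader might join the 48-hour definition in SAP 8.2 to the null rule in 7.2 and infer that the SAP leaves this subject with no recovery time. The documents do not support that: the null is for subjects who never reach the level, and this one did.

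Second, the infusion and observation rules keep many recoverers in hospital long enough, and the eligibility criteria exclude short expected stays and patients already improving. This also stands. Early discharge is possible and unaddressed, but nothing shows it to be typical.

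Third, a reader might infer that an efficacy signal would be hidden or reversed. That goes too far. The unequal-discharge examples rest on assumed rates, time to discharge and OSCI change are summarized separately (SAP 8.3.6, 8.3.7), and the endpoint data are listed.

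Fourth, counting early discharges as recovered credits stability nobody observed, although both documents bar imputation. This is a real cost. However, protocol 7.1 allows exceptions stated in 7.2.1, and a rule written into the event definition is open to inspection in a way that silence is not.

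What the reply does not remove is the SAP's conflict with its own definition. If 7.2 is corrected to match 4.2 and 8.2, the protocol's discharge gap enters the analysis that will be run.

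**Conclusion.** The point holds in two linked parts. Protocol 7.2.1 has no rule for discharge before 48 hours are confirmed, so a subject who goes home on room air within that time is scored like a death or a non-recoverer. This follows from the definition, the end of SpO2 collection and silence on discharge; the protocol does not name discharge as failure. The SAP states a 48-hour endpoint and derives a first-reading endpoint without declaring the change.

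The effect is confined to descriptive summaries. Its size cannot be estimated, since the documents give neither an early-discharge rate nor a rate of transient readings. The percentages above show direction and scale under assumption only. The 33-point figure depends only on the planned three-subject arms. The matter should be corrected because the summaries are small and the two parts must be repaired together.

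**What to change.** State one event definition in protocol 7.2.1 and SAP 4.2, 7.2, 8.2 and 8.2.6 that keeps the 48-hour condition, and record it in SAP section 6. Add a discharge rule. A subject counts as achieving the endpoint, on the first day of the final room-air run, if all of these hold:

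- discharged alive without supplemental oxygen;
- every recorded room-air SpO2 from the start of that run to discharge is at least 94%;
- no return to oxygen or readmission is recorded within 48 hours.

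Show two sensitivity summaries: the strict version, requiring 48 hours observed in hospital, and the first-reading version now in SAP 7.2. Do not censor subjects sent home on oxygen at the date of discharge, because leaving hospital is related to prognosis and that censoring may be informative.

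The cost is wording and one derivation from discharge dates, respiratory records and Telemed data that the plan already collects. If the database is already locked, label the new summary post hoc. The downside is that up to 48 hours of stability is assumed, not observed, for early discharges; the strict version shows how much rests on that.
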